**Table 10–2: Required investigations and follow up for PDILI**

Laboratory value					
ALT or AST	Total bilirubin	Symptoms a of hepatitis or hypersensitivity	Consultation requirements	Required testing	Continued evaluation
Requires immediate and permanent IMP discontinuation					
≥3xULN	<2xULN	No	Medical Monitor must be notified within 24 hours (eg, by laboratory alert) and study participant discussed with Medical Monitor ASAP.	Must have repeat liver chemistry values and additional testing completed ASAP (see Section 10.2.1.3 ); recommended to occur within 24 hours at Phase 1 unit or with HCP.	Monitoring of liver chemistry values required once per week until values normalize, stabilize, or return to within Baseline values. b
≥3xULN	NA	Yes	Hepatology consult. c		Monitoring of liver chemistry values required at least twice per week until values normalize, stabilize, or return to within Baseline values. b
≥3xULN	≥2xULN d	NA	Medical Monitor must be notified within 24 hours (eg, by laboratory alert) and study participant discussed with Medical Monitor ASAP.		

ALP=alkaline phosphatase; ALT=alanine aminotransferase; ASAP=as soon as possible; AST=aspartate aminotransferase; HCP=healthcare practitioner; IMP=investigational medicinal product; NA=not applicable; PDILI=potential drug-induced liver injury; ULN=upper limit of normal

a Hepatitis symptoms include fatigue, nausea, vomiting, and right upper quadrant pain or tenderness; hypersensitivity symptoms include eosinophilia (>5%), rash, and fever (without clear alternative cause).

b Unless an alternative monitoring schedule is agreed by the Investigator and UCB responsible physician. Determination of stabilization is at the discretion of the Investigator in consultation with the hepatologist (as applicable) and UCB responsible physician, as needed.

c Details provided in [Section 10.2.1.1](#). The local hepatologist is the expert usually consulted by the treating physician for assessment and management of potential hepatic disease. This would usually be a hepatologist, but may be a gastroenterologist.

d If the study participant also has ≥2xULN ALP, the possibility of an indication of biliary obstruction should be discussed with the Medical Monitor.

### **10.2.1.1 Consultation with Medical Monitor and local hepatologist**

Potential drug-induced liver injury events require notification of the Medical Monitor within 24 hours (eg, by laboratory alert), and the study participant must be discussed with the Medical Monitor as soon as possible. If required, the study participant must also be discussed with the local hepatologist. The local hepatologist is the expert usually consulted by the treating physician for assessment and management of potential hepatic disease. This would usually be a hepatologist, but may be a gastroenterologist. If determined necessary, this discussion should be followed by a full hepatology assessment (see [Section 10.2.1.3](#)) and SAE report (if applicable).

### **10.2.1.2 Immediate action: determination of investigational medicinal product discontinuation**

All PDILI events require immediate action, testing, and monitoring.

The immediate action is dependent on the laboratory values and symptoms of hepatitis or hypersensitivity and requires permanent IMP discontinuation (see [Section 6.4.1](#) and [Table 10–2](#) for details).

When IMP is discontinued, all concomitant medications and herbal supplements that are not medically necessary should also be discontinued. The Investigator should also consider dose reduction for medically necessary concomitant medication and consider changing any medically required concomitant medication known to be hepatotoxic to a suitable alternative.

### **10.2.1.3 Testing: identification/exclusion of alternative etiology**

The measurements and additional information required for the assessment of PDILI events when there is a reasonable possibility that they may have been caused by the IMP are detailed in [Table 10–3](#) (laboratory measurements) and [Table 10–4](#) (additional information). Results of the laboratory measurements and information collected are to be submitted to the Sponsor on the corresponding eCRF. If the medical history of the study participant indicates a requirement for other assessments not included below, these additional assessments should be completed and submitted, as applicable.

The following measurements are to be assessed:

**Table 10–3: PDILI laboratory measurements**

Virology-related	Hepatitis A IgM antibody
	HBsAg
	Hepatitis E IgM antibody
	HBcAb-IgM
	Hepatitis C RNA
	Cytomegalovirus IgM antibody
	Epstein-Barr viral capsid antigen IgM antibody (if unavailable, obtain heterophile antibody or monospot testing)
Immunology	Anti-nuclear antibody (qualitative and quantitative)
	Anti-smooth muscle antibody (qualitative and quantitative)
	Type 1 anti-liver kidney microsomal antibodies (qualitative and quantitative)
Hematology	Eosinophil count
Urinalysis	Toxicology screen
Chemistry	Amylase
	If total bilirubin $\geq 1.5 \times \text{ULN}$ , obtain fractionated bilirubin to obtain % direct bilirubin
	Serum CPK and LDH to evaluate possible muscle injury causing transaminase elevation
Additional	Prothrombin time/INR a
	Serum pregnancy test
	PK sample

ALT=alanine aminotransferase; CPK=creatine phosphokinase; HBcAb-IgM=hepatitis B core antibody-IgM; HBsAg=hepatitis B surface antigen; IgM=immunoglobulin M; INR=international normalized ratio; LDH=lactate dehydrogenase; PDILI=potential drug-induced liver injury; PK=pharmacokinetic; RNA=ribonucleic acid; ULN=upper limit of normal

a Measured only for study participants with ALT >8xULN, elevations in total bilirubin, and symptoms of hepatitis or hypersensitivity. Hepatitis symptoms include fatigue, nausea, vomiting, and right upper quadrant pain or tenderness; hypersensitivity symptoms include eosinophilia (>5%), rash, and fever (without clear alternative cause).

The following additional information is to be collected:

**Table 10–4: PDILI information to be collected**

New or updated information
Concomitant prescription and over-the-counter medications (eg, acetaminophen, herbal remedies, vitamins); dosages and dates should be included.
Pertinent medical history, including the following: 
 
• History of liver disease (eg, autoimmune hepatitis, nonalcoholic steatohepatitis or other “fatty liver disease”)
 
• Adverse reactions to drugs
 
• Allergies
 
• Relevant family history or inheritable disorders (eg, Gilbert’s syndrome, alpha-1 antitrypsin deficiency)
 
• Recent travel
 
• Progression of malignancy involving the liver (Note: Metastatic disease to the liver, by itself, should not be used as an explanation for significant AST and/or ALT elevations.)
 

The appearance or worsening of clinical symptoms of hepatitis or hypersensitivity (eg, fatigue, nausea, vomiting, right upper quadrant pain or tenderness, decreased appetite, abdominal pain, jaundice, fever, or rash)
Recent clinically significant hypotension or hypoxemia with compromised cardiopulmonary function
Alcohol and illicit drug use
Results of liver imaging or liver biopsy, if done
Results of any specialist or hepatology consult, if done
Any postmortem/pathology reports

ALT=alanine aminotransferase; AST=aspartate aminotransferase; PDILI=potential drug-induced liver injury

**10.2.1.4 Follow-up evaluation**

Potential drug-induced liver injury events require follow-up monitoring as described in [Table 10–2](#). Monitoring should continue until liver chemistry values normalize, stabilize, or return to baseline. Determination of stabilization is at the discretion of the Investigator in consultation with the hepatologist (as applicable) and UCB responsible physician, as needed.

**10.2.1.5 Optional hepatic investigation sample collection**

If a study participant is undergoing further investigation for PDILI and has consented to retrospective genetic analysis per local regulations, the study participant’s blood sample will be shipped to a secure storage facility. The blood sample will be retained in the UCB Hepatic Investigation Biobank to solely support retrospective genetic analyses associated with an adverse therapeutic response to PSL.

Genetic analyses of deoxyribonucleic acid isolated from the blood will be contracted by UCB to specialized third-party laboratories and analysis will be limited to:

- Uridine 5'-diphospho-glucuronosyltransferase loci – the loci responsible for Gilbert's syndrome (hyperbilirubinemia)
- Human leukocyte antigen (HLA) loci – for example, HLA-B5701 that has been associated with abacavir- and flucloxacillin-induced liver injury
- Absorption, distribution, metabolism, and excretion gene loci associated with abnormal pharmacokinetics

Genetic analysis of samples may be performed immediately, on a per-study basis, or as part of combined analyses across multiple studies belonging to the same clinical development program. As a result, samples will be retained for 15 years unless clinical development of the IMP is terminated, at which point all samples will be destroyed. The results determined using clinically approved diagnostic tests will be made available to the Investigator upon request.

Study participants may request at any time that their sample be removed from the UCB Hepatic Investigation Biobank and destroyed, though data from analyses already performed will remain on file. All samples, associated materials, and data will be kept securely by UCB and its agents. A sample destruction request should be made in writing to the Investigator who will notify the UCB Biorepository Manager (Global Exploratory Development, UCB, [name]).

### **10.3 Other safety measurements**

#### **10.3.1 Physical examination**

Full physical examinations will be performed at the time points specified in [Table 5-1](#). Full physical examinations will include cardiac and respiratory function via auscultation and review of the following body systems: general appearance; ear, nose, and throat; eyes; hair and skin; respiratory; cardiovascular; gastrointestinal; musculoskeletal; hepatic; neurological; and mental status.

Abbreviated physical examinations will be performed at the time points specified in [Table 5-1](#). These abbreviated physical examinations will include a review of the following body systems: general appearance; skin; respiratory; cardiovascular; gastrointestinal; hepatic; and mental status.

Height (study participant without shoes, and height rounded to the nearest 0.5cm) and body weight (study participant in underwear or light clothing, without shoes and rounded to the nearest 0.1kg) will be recorded at the Screening Visit and BMI will be derived ( $\text{kg}/[\text{height (m)}]^2$ ).

#### **10.3.2 Vital signs**

Vital signs (pulse rate, BP, respiratory rate, and body temperature) will be recorded at the time points shown in [Table 5-1](#).

For the purposes of assessing the inclusion criterion, at the Screening Visit and the Baseline Visit, BP measurements will be performed in both supine and standing positions according to the following procedure: Measure supine BP after the study participant has been lying down for 10 minutes, then ask the study participant to stand up and record the standing BP

after 1 minute and 3 minutes. At all time points after the Screening Visit, BP will only be measured in the supine position, ie, there will be no assessment for orthostatic hypotension.

By decision of the Sponsor and the Investigator, the time points specified in [Table 5-1](#) may be modified based on preliminary safety and PK assessments from previous doses tested in the study.

### **10.3.3 Standard 12-lead electrocardiogram**

Triplicate standard 12-lead ECGs (RR interval, PR interval, QRS interval, QT, QTcB, and QTcF) will be recorded at times specified in [Table 5-1](#), according to the following procedure: study participant lies in a supine position for  $\geq 5$  minutes; then a 12-lead ECG will be recorded in the same position. All ECG recordings will be performed in triplicate at 2- to 3-minute intervals.

Electrocardiograms will be recorded at a speed of 25mm/s and with a calibration of 1cm/mV.

The times specified in [Table 5-1](#) include a series of ‘triplicate 12-lead ECG run-in days’ to be performed 1 day prior to first PSL or erythromycin dose in Treatment Periods 1, 2, and 3 (that is, Day -1, Day 11, Day 22, and Day 25). On these days, triplicate standard 12-lead ECGs will be performed for each of the following matching time points: predose, 1h, 2h, 3h, and 6h postdose for the morning administration of PSL and/or erythromycin, and 0.5h predose for the evening administration of PSL and/or erythromycin.

By decision of the Sponsor and the Investigator, the time points specified in [Table 5-1](#) may be modified based on preliminary safety and PK assessments from previous doses tested in the study.

The Investigator or designee will determine whether the results of the ECG are normal or abnormal. All important abnormalities should be reported. The original ECG tracing will be signed or initialled, and dated by the Investigator or designee, and will be retained at the clinical site as part of the Investigator’s Site File. The original electronic file of the ECG tracing will be transferred to UCB and will remain available at least until the approval of the clinical study report.

### **10.3.4 Assessment of suicidality**

The C-SSRS will be completed at the scheduled time points presented in [Table 5-1](#).

Suicidality will be assessed by trained study personnel using the C-SSRS (Posner et al, 2011). This scale will be used for screening as well as to assess suicidal ideation and behavior that may occur during the study. The Investigator’s decision about study participant continuation in the study or study participant withdrawal from the study if the study participant has a positive response to the CSSRS Question 4, should be based on the benefit/risk balance for continuation or discontinuation of study treatment in view of the individual study participant circumstances, condition, attained efficacy, causality, alternative risk management options, etc.

If an additional visit (or unscheduled visit) is conducted due to safety or efficacy reasons, a C-SSRS assessment will be performed with the study participant during the visit. If an additional visit (or unscheduled visit) is conducted for reasons other than safety or efficacy concerns (eg, replacement of lost medication, repeated collection of a laboratory specimen due to collection or analysis issues), a C-SSRS will not be required at these visits.

Details of the case must be documented by the Investigator (PI or designee, not site staff conducting the C-SSRS) and provided to UCB via the SAE reporting process.

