Despite the occurrence of ECG findings such as ectopies (asymptomatic, not requiring clinical intervention), there are no current data suggesting that PSL has an adverse effect on cardiovascular function other than a minimal lowering effect on BP. The degrees of reduction of both supine blood pressure (SBP) and diastolic blood pressure (DBP) are consistent with the GABAA-targeted mechanism of action of PSL and do not appear likely to have a clinically significant effect in therapeutic use. As a precaution from preclinical and clinical findings of non-clinically significant ECG abnormalities and hypotension, ECGs and vitals are being assessed frequently in current clinical studies.

There is no benefit for healthy study participants to participate in this study. However, the information obtained from this study will inform decisions on safe and effective doses of PSL to be given to epileptic study participants in future studies. The Sponsor will immediately notify the Principal Investigator (PI) and regulatory agencies if any additional safety or toxicology information becomes available during the study.

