## 6.2 Exclusion criteria

Study participants are not permitted to enroll in the study if any of the following criteria is met:

1. Study participant has previously received IMP in this study.
2. Study participant has participated in another study of an IMP (or a medical device) within the previous 3 months before Screening (or within 5 half-lives for the IMP, whichever is longer) or is currently participating in another study of an IMP (or a medical device).
3. Study participant has a history of drug or alcohol dependency within the previous 6 months or tests positive for alcohol (breath test) and/or drugs of abuse (urine test) at the Screening Visit.
4. Study participant has a current or past psychiatric condition that, in the opinion of the Investigator, could compromise his/her safety or ability to participate in this study or a history of schizophrenia, or other psychotic disorder, bipolar disorder, or severe unipolar depression. The presence of potential psychiatric exclusion criteria will be determined based on the psychiatric history collected at Screening.
5. Study participant has a lifetime history of suicide attempt (including an [REDACTED]), or [REDACTED] as indicated by a positive response (“Yes”) to either Question 4 or Question 5 of the “Screening/Baseline” version of the C-SSRS at Screening.
6. Study participant has any medical condition that, in the opinion of the Investigator, could jeopardize or would compromise the study participant’s ability to participate in this study.
7. Study participant has a known hypersensitivity to any components of the IMP as stated in this protocol.
8. Study participant has made a blood or plasma donation or has had a comparable blood loss (>400mL) within the last 3 months prior to the Screening Visit.
9. Study participant has a consumption of more than 3 units of alcohol/day in case of females, more than 4 units of alcohol/day in case of males.
10. Study participant smokes more than 5 cigarettes per day (or equivalent) or has done so within 6 months prior to the Screening Visit.
11. Study participant has a consumption of more than 600mg of caffeine/day (200mL of coffee contains approximately 100mg of caffeine, 200mL of black tea approximately 30mg, and 200mL of cola approximately 20mg).
12. Study participant has a diet, which deviates notably from the “normal” amounts of protein, carbohydrate, and fat, as judged by the investigator (eg, vegetarians or vegans).

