### 6.3 Withdrawal criteria

Study participants are free to withdraw from the study at any time, without prejudice to their continued care.

Study participants must be withdrawn from the study if any of the following events occur:

1. Study participant develops a clinically relevant medical condition (or laboratory parameter) that, in the opinion of the Investigator, jeopardizes or compromises the study participant's ability to participate in this study or makes it unsafe to continue (for example a psychiatric event).
2. Study participant withdraws his/her consent.
3. The Sponsor or a regulatory agency requests withdrawal of the study participant.
4. An ECG shows an absolute QTcF value  $>500\text{ms}$  or  $>60\text{ms}$  prolongation above Baseline (defined as the mean of triplicate ECG taken at predose on Day 1, Day 12, Day 23 or Day 26) in 1 or more ECG recordings.
5. Study participant develops second- or third-degree atrioventricular block or another clinically relevant change in ECG results as determined by the Investigator.
6. Refer to [Section 6.4.1](#) for withdrawal criteria in relation to potential drug-induced liver injury (PDILI).
7. Study participant tests positive for pregnancy at any point during the study.

Study participants may be withdrawn from the study if any of the following events occur:

8. Study participant is noncompliant with the study procedures or IMP in the opinion of the Investigator.
9. Study participant takes prohibited concomitant medications as defined in this protocol.

If the withdrawal occurs following dosing with IMP, the study participant will be asked to return for the EOS Visit 7 to 10 days after last intake of IMP.

The Investigator should attempt to obtain information on study participants in the case of withdrawal or discontinuation. For study participants considered as lost to follow up, the Investigator should make an effort (at least 1 phone call and 1 written message to the study participant), and document his/her effort (date and summary of the phone call and copy of the written message in the source documents), to complete the final evaluation. All results of these evaluations and observations, together with a narrative description of the reason(s) for removing the study participant, must be recorded in the source documents. The electronic Case Report form (eCRF) must document the primary reason for withdrawal or discontinuation.

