8 EFFICACY ANALYSES

Not applicable.

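### After a positive on-study C-SSRS Question 4, Section 10.3.4 has the Investigator weigh benefit and efficacy that healthy volunteers cannot have, and it names no action for Question 5 or suicidal behaviour

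*Protocol*

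**What the plan says.** Protocol Section 10.3.4 uses the C-SSRS both for screening and to detect suicidal ideation and behaviour during the study. Its only decision rule is that the Investigator's choice after a "positive response to the CSSRS Question 4, should be based on the benefit/risk balance for continuation or discontinuation of study treatment". The considerations listed for that choice include "condition, attained efficacy, causality, alternative risk management options, etc". The section closes by requiring that details of the case be documented and "provided to UCB via the SAE reporting process".

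Four other places bear on this:

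- Protocol Section 2.3: "There is no benefit for healthy study participants to participate in this study".
- SAP, under "8 EFFICACY ANALYSES": marked as not applicable.
- Protocol Section 6.2, exclusion 5: a lifetime suicide attempt bars entry, and so does a positive answer at Screening "to either Question 4 or Question 5 of the" C-SSRS. Parts of this criterion are blacked out, but the naming of the two questions is legible.
- Protocol Section 6.3, criterion 1: withdrawal is mandatory for a clinically relevant condition "that, in the opinion of the Investigator, jeopardizes or compromises" the ability to take part, or that "makes it unsafe to continue (for example a psychiatric event").

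No C-SSRS item is named in the withdrawal criteria (6.3) or the stopping rules (6.4). SAP Section 10.4.3.2 only lists C-SSRS responses.

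**The concern.** The one on-study rule that names a C-SSRS item does not suit this population. A benefit/risk balance makes sense for a patient whose seizures are controlled by the drug. A healthy volunteer has nothing on the benefit side, yet the text still presents continued dosing as an option after an answer that would have kept the person out of the study. For Question 5 and for suicidal behaviour the Investigator has only the general criteria.

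The stake is participant safety. Section 2.3 reports acute psychiatric SAEs in 3 participants given padsevonil and asks for vigilance. The C-SSRS is done daily from Day 26 to Day 33, during coadministration, when Section 5.9 expects padsevonil exposure to rise about 3.7-fold. The plan therefore asks the question most often when exposure is expected to be highest, without saying what a positive answer requires.

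**Working it through.** The plan states no figure on this point, so the main check sets the rules side by side.

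| Finding | At entry (6.2, exclusion 5) | On study (10.3.4) |
|---|---|---|
| Question 4 positive | Excluded | Continue or withdraw, on a benefit/risk balance |
| Question 5 positive | Excluded | No action named |
| Suicidal behaviour | Lifetime attempt excludes | No action named |

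**Do the listed considerations have content?** Benefit: none, by Section 2.3. Efficacy: not analysed, by SAP Section 8. What remains is risk, causality and risk management. Section 10.3.4 also gives replacement of lost medication as a reason for an extra visit, although Section 7.7 has every dose supervised. This suggests wording carried over from a patient study.

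**How are other safety findings handled?** With fixed limits. QTcF above 500 ms or more than 60 ms above Baseline requires withdrawal, as does a positive pregnancy test (6.3). ALT or AST at or above 3xULN requires permanent IMP discontinuation (6.4.1). Suicidality has no equivalent.

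**When can the question arise?** Assessments after first dose, from Table 5-1 footnote f:

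- D7, D10, D18, D21: 4
- D26 to D33: 8
- D34, D37: 2
- D38, EOS: 2
- Total: 4 + 8 + 2 + 2 = 16

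The last padsevonil dose is on the morning of D33 and the last erythromycin dose is on D37. The C-SSRS on D26 to D34 and on D37 precedes the morning dose. So:

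- Any dose still due: 16 − 2 (D38, EOS) = 14
- Padsevonil still due: 4 + 8 = 12
- Erythromycin only: 2 (D34, D37)

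Planned padsevonil doses are 4×2 + 1 = 9 in Period 1, 9 in Period 2 and 7×2 + 1 = 15 in Period 3b. Erythromycin runs from D23 to D37, 15×2 = 30 doses. Doses still due at selected assessments:

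| Assessment | Padsevonil | Erythromycin |
|---|---|---|
| D7 | 9 + 15 = 24 | 30 |
| D26, predose | 15 | 12×2 = 24 |
| D33, predose | 1 | 5×2 = 10 |
| D37, predose | 0 | 2 |

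The grid of Table 5-1 also marks the C-SSRS in the Day 23 to 25 column, but footnote f and Section 8.4.1.1 list none there. The counts follow the footnote. They describe opportunity, not likelihood.

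**The case against.** A reader might infer that the protocol lets a suicidal volunteer go on being dosed with no safeguard. The documents do not support that:

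- Section 6.3 criterion 1 is mandatory and gives a psychiatric event as its example; active suicidal ideation fits it naturally.
- Criterion 3 lets the Sponsor or a regulatory agency require withdrawal.
- Section 10.3.4 sends case details through the SAE route, for which Section 10.1.2.3 sets 24-hour notification.
- Section 6.4 stops dosing for all participants after one SAE at least possibly related to IMP, with restart only after MHRA and REC approval of an amendment.
- Section 11.1 allows immediate protective action.

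With no benefit to weigh, the balance in 10.3.4 itself leans towards withdrawal, and efficacy is only one entry in an open list.

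Most of this stands, and it is why the point is minor. It does not close the gap. Criterion 1 turns on the Investigator's opinion. Criterion 3 depends on a request. Section 6.4 applies only if the event is judged serious and related. SAE reporting is not a dosing decision, and the case to be reported is not defined. None of these says what a positive Question 4, Question 5 or behaviour item requires.

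A second objection is that an automatic stop has its own risk. Section 2.3 notes that one healthy participant with a psychiatric SAE worsened on abrupt discontinuation, that a withdrawal syndrome is possible, and that titration and taper are the intended mitigation. This is a good reason to add assessment and observation to the rule. It is not a reason to keep dosing: padsevonil ends without taper in every period here, and the other mandatory withdrawals also stop it.

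**Conclusion.** The point holds as a minor design correction. Section 10.3.4 applies a benefit and efficacy test that has no content in this population, and it names no action for Question 5 or suicidal behaviour although the entry rule covers both questions and past attempts. What is missing is an explicit requirement, not all protection; the general safeguards make withdrawal likely.

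A reader might also infer a threat to the trial's results. There is none: no PK endpoint, model or safety summary depends on this wording.

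The decision could arise at 14 of 16 scheduled assessments, 12 with padsevonil still due. How often it would arise cannot be estimated from the documents. The conclusion assumes that footnote f, rather than the grid, gives the C-SSRS schedule, and that the blacked-out words in exclusion 5 do not change the legible reference to Questions 4 and 5. Section 10.3.4 carries no redaction mark.

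**What to change.** In Section 10.3.4, delete the benefit and efficacy wording. Replace it with a rule along these lines, cross-referenced in Section 6.3:

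- A positive on-study response to C-SSRS Question 4 or Question 5, or any reported suicidal behaviour, requires permanent IMP discontinuation and prompt referral for psychiatric assessment.
- The participant stays under observation until judged safe for discharge, including for symptoms after abrupt discontinuation.
- The participant is then withdrawn, with the EOS safety follow-up of Section 6.3.

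Stopping IMP first and withdrawing only after assessment follows the pattern already used for liver injury in Section 6.4.1. Withdrawal with the EOS visit alone would be too little, because that visit comes 7 to 10 days after the last dose.

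The cost is a few sentences, with no new scheduled assessment and no change to the analysis. Referral and observation arise only if the rule is triggered. Under footnotes d to f and Sections 8.3 and 8.4, participants are in the unit at all 14 assessments where dosing is still pending, so observation is practicable. The downside is the possible loss of a rare participant from the PK set, within the planned margin of 28 − 20 = 8.
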